7.3.2 Formulation of Control Product

N/A (open-label study).

7.3.3 Packaging and Labeling

Refer to DAXXIFY Package Insert.

7.4 Supply of Study Drug at the Site

7.4.1 Dosage/Dosage Regimen

Subject's Current* BotoxA Dose	DAXI Dose 1	DAXI Dose 2
-----------------------------------	-------------	-------------

0.625 units unilateral	0.625 unit	0.625 unit
1.25 units unilateral	1.25 units	1.25 units
2.5 units unilateral	2.5 units	2.5 units
0.625 units bilateral	0.625 unit	0.625 unit (contralateral)
1.25 units bilateral	1.25 units	1.25 units (contralateral)
2.5 units bilateral	2.5 units	2.5 units (contralateral)

*Current is defined as the average of subject's last 3 injections

7.4.2 Dispensing

DAXI will be received at the UCSF Voice and Swallowing Center. DAXI will be kept in a locked cabinet and refrigerator at the UCSF Voice and Swallowing Center with a log kept for usage.

7.4.3 Administration Instructions

DAXI will be reconstituted using sterile unpreserved saline into 1mL syringes within 2 hours of injection by a trained preparer. It will then be injected into the unilateral or bilateral thyroarytenoid/lateral cricoarytenoid (TA-LCA) complex using electromyographic (EMG) guidance.

Laterality of injection with DAXI will be dependent on the subject's usual injection pattern. If the patient has traditionally been injected on one side, DAXI will be injected on the same side. If the patient has traditionally been injected unilaterally but with alternating sides, DAXI injection will follow the alternating pattern. If the patient has traditionally received bilateral injections, DAXI will first be injected on the left side, and if a second dose is required, it will be injected on the right.

Laterality Rules

Traditionally unilateral	DAXI same side	
Traditionally unilateral/alternating	DAXI continues in sequence	
Traditionally bilateral	1 st DAXI left	2 nd DAXI right

7.5 Supply of Study Drug at the Site

The study drug is supplied by the research team.

7.5.1 Storage

Refer to DAXXIFY Package Insert.

7.6 Study Drug Accountability

An accurate and current accounting of the dispensing and return of study drug for each subject will be maintained on an ongoing basis by a member of the study site staff.

7.7 Measures of Treatment Compliance

There is no treatment compliance because DAXI is an injectable medication. No DAXI goes home with participants.

8 STUDY PROCEDURES AND GUIDELINES

A Schedule of Events representing the required testing procedures to be performed for the duration of the study is diagrammed in Appendix 1.

Prior to conducting any study-related activities, written informed consent and the Health Insurance Portability and Accountability Act (HIPAA) authorization must be signed and dated by the subject or subject's legal representative.

8.1 Clinical Assessments

8.1.1 Concomitant Medications

No concomitant medications.

8.1.2 Demographics

Demographic information (date of birth, gender, race) will be recorded at Screening.

8.1.3 Medical History

Relevant medical history, including history of current disease, other pertinent respiratory history, and information regarding underlying diseases will be recorded at Screening.

8.1.4 Physical Examination

A physical examination will be performed by either the investigator or a sub-investigator who is a physician at Visit # 1. New abnormal physical exam findings must be documented.

8.1.5 Vital Signs

N/A

8.1.6 Oximetry

N/A

8.1.7 Spirometry

N/A

8.1.8 Other Clinical Procedures

N/A

8.1.9 Adverse Events

Information regarding occurrence of adverse events will be captured throughout the study. Duration (start and stop dates), severity/grade, outcome, treatment and relation to study drug will be recorded on the case report form (CRF).

8.2 Clinical Laboratory Measurements

8.2.1 Hematology

N/A

8.2.2 Blood Chemistry Profile

N/A

8.2.3 Pregnancy Test

A urine pregnancy test will be obtained from female participants who are of childbearing age prior to their participation in the study at Visit 1.

8.2.4 Urinalysis

N/A

8.3 Pharmacokinetic Measurements

N/A

8.4 Research Laboratory Measurements

N/A

8.4.1 Cell Count and Differential

N/A

8.4.2 Sputum Cytokine Measurements

N/A

9 EVALUATIONS BY VISIT

9.1 Phone Screening (7 Days prior to injection)

1. Confirmation participants meet all inclusion criteria and no exclusion criteria review
2. If they have provided consent to contact, reach out and explain the study to them.
3. Review the study with the subject (subject's legal representative) and obtain written informed consent and HIPAA authorization via DocuSign.
4. Assign the subject a unique screening number.
5. Record demographics data.
6. Record medical history, including history of ADLD, diagnosis date, and prior Botox treatments.
7. Patient fills out baseline PROMs electronically through Qualtrics (VHI-10, CPIB-10, OMNI-VES, EAT-10)
8. Patient records their voice in Phonalyze for CPP and CAPE-V analysis

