5 CRITERIA FOR EVALUATION

5.1 Primary Efficacy Endpoint

The primary efficacy endpoint is the difference in VHI-10 scores at 8 weeks after injection with DAXI. VHI-10 questionnaires will be given at baseline, day 14, then monthly.

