9.2 Visit 1 (Clinic Visit, Day 0)

1. Review of birth control history with female participants of childbearing potential.
2. For women of childbearing potential, counsel participants to use adequate birth control methods required during the trial to avoid pregnancy.
3. For women of childbearing potential, urine pregnancy test will be checked prior to injection.
4. Perform a complete physical examination.
5. Perform DAXI injection. Laterality of injection with DAXI will be dependent on the subject's usual injection pattern. If the patient has traditionally been injected on one side, DAXI will be injected on that same

side. If the patient has traditionally been injected unilaterally but with alternating sides, DAXI injection will follow the alternating pattern. If the patient has traditionally received bilateral injections, DAXI will first be injected on the LEFT side, and if a second dose is required, it will be injected on the right.

6. Record any Adverse Experiences during injection
7. Schedule participant for remote follow-up visit in 5 days.

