14.3 Analysis of Primary Endpoint

Our primary outcome is the difference in VHI-10 score at 8 weeks after injection with DAXI. This will be determined using a paired t-test with subjects pre-treatment VHI-10 scores as a control. Our second primary outcome measure is the duration of effect of DAXI, assessed qualitatively through phone calls, compared to patients' prior Botox treatment. We will produce a Kaplan-Meier curve to illustrate the duration of clinical benefit after treatment with DAXI.

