14.4 Analysis of Secondary Endpoints

A secondary outcome will be comparing the duration of effect of DAXI with patients' prior Botox treatment. Specifically, we will determine the median time to baseline VHI-10 after treatment with DAXI and produce a Kaplan-Meier curve to illustrate the duration of clinical benefit.

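### VHI-10 is scored only once before treatment, at phone screening; a second score on Day 0 would cheaply steady the baseline that both VHI-10 endpoints rest on

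*Combined protocol and SAP*

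**What the plan says.** The baseline questionnaires belong to the step headed "9.1 Phone Screening (7 Days prior to injection", where item 7 reads "Patient fills out baseline PROMs electronically through Qualtrics" and names VHI-10 among them. The Day 0 list in section 9.2 covers contraception review and counselling, a pregnancy test where applicable, a physical examination, the injection, adverse-event recording and scheduling. It contains no VHI-10. Appendix 1 agrees: VHI-10 is marked at Screening, Visit 4 and Visits 5-10, and is blank at Visit 1. The clinician-rated USDRS is marked at Visit 1, so that scale has a Day 0 value and the primary outcome does not.

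Section 5.1 says only "VHI-10 questionnaires will be given at baseline, day 14, then monthly" and does not define baseline further. On the analysis, section 14.3 says "This will be determined using a paired t-test with subjects pre-treatment VHI-10 scores as a control". The duration endpoint in section 14.4 is the "median time to baseline VHI-10 after treatment with DAXI". No section provides a repeat baseline, a run-in, a tolerance around baseline or a rule that a return must be confirmed.

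**The concern.** The trial has one arm, so the pre-treatment score is the only comparator for the 8-week VHI-10. The same number is then reused as the patient's own cut-off at every later monthly survey. Random error in it does not bias the mean difference, but it widens the interval. It also shifts an individual's threshold: a score that is too low by chance brings the apparent return forward, and one that is too high delays it.

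The score also precedes time zero. The gap is about 7 days for a patient injected once. Section 9.4 allows a second injection on Day 7-14, and section 9.6 counts the monthly surveys from the most recent injection. For re-injected patients the baseline is therefore about 7 + 7 = 14 to 7 + 14 = 21 days before the reference injection. Every patient attends clinic on Day 0, and a pre-treatment score cannot be recovered after injection.

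**Working it through.** **Inputs from section 14.6.** n = 20; SD of the paired difference about 10; detectable difference 6.6; alpha 0.05; pre-treatment SD 7.09 and 6-week SD 7.24 in the cited Botox study. **Assumed:** test-retest correlation r of 0.7, 0.8 or 0.9 for two untreated scores a week apart.

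**1. The plan's own figure.** Two-sided paired t-test, 19 df, noncentrality 6.6 / (10/√20) = 2.95: power 79.9%. The difference detectable with 80% power is 6.60. Both match the plan.

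**2. Effect of a second baseline score on the primary test.** Replacing one score by the mean of two removes half the error variance of the baseline:

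Var(change) = 10² − 7.09² × (1 − r)/2

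| r | Variance | SD | Detectable difference | Reduction | Power at 6.6 |
|---|---|---|---|---|---|
| one score | 100 | 10 | 6.60 | – | 79.9% |
| 0.7 | 100 − 7.54 | 9.62 | 6.35 | 3.8% | 82.9% |
| 0.8 | 100 − 5.03 | 9.75 | 6.44 | 2.5% | 81.9% |
| 0.9 | 100 − 2.51 | 9.87 | 6.52 | 1.3% | 80.9% |

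**3. Error in the individual baseline.** The error SD is s = 7.09 × √(1 − r) with one score and s/√2 with two: 3.88 to 2.75 (r = 0.7), 3.17 to 2.24 (0.8), 2.24 to 1.59 (0.9).

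**4. False return to baseline.** Suppose a patient keeps a constant true benefit of 6.6 points over four monthly surveys. Errors are normal and independent, with SD s at each survey, and a return is counted when a survey score reaches the baseline score. With baseline error b, the chance of at least one false return is the average over b of 1 − Φ((b + 6.6)/s)⁴. Here b has SD s (one score) or s/√2 (mean of two).

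| r | One score | Mean of two |
|---|---|---|
| 0.7 | 28.9% | 24.7% |
| 0.8 | 19.4% | 14.5% |
| 0.9 | 6.0% | 3.0% |

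**5. Late recognition.** If the benefit has gone completely, the chance that three surveys in a row all stay below the baseline score is 1/4 with one baseline score, since the baseline must then be the largest of four exchangeable values. With the mean of two it is about 21%. Neither figure depends on r.

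**The case against.** The strongest reply is that nothing here is wrong. A single pre-treatment score is a common choice, the stated power reproduces, and baseline noise already sits inside the SD of 10. That stands. A reader might infer that the primary test is underpowered because its baseline is noisy; the documents do not support that.

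A reader might also expect a larger gain by setting aside the SD of 10 and combining 7.09 and 7.24 with a substantial pre-post correlation. With that correlation and r both at 0.7, the detectable difference falls from 3.67 to 3.19, about 13%. That is a boundary case: if both scores have reliability 0.7, the true scores correlate 0.7/0.7 = 1. The plan's SD of 10 instead implies a correlation of (7.09² + 7.24² − 10²)/(2 × 7.09 × 7.24) = 0.03. On the plan's own input the gain is 1-4%.

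The most tempting reading is that a Day 0 score would supply the untreated comparison that a single-arm trial lacks, or would expose regression to the mean. It would not. About one week in 20 patients says little about eight untreated weeks. VHI-10 is also not an entry criterion (sections 5.6 and 5.7), so regression to the mean through selection is limited. Drift before injection could go either way.

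Two practical objections carry weight. If scores shift between screening and Day 0, their mean is neither the screening nor the time-zero value. And a form completed in clinic just before injection differs in setting from the remote follow-up forms, so the change between the two scores may mix setting and anticipation with true change. Finally, most false returns remain at r = 0.7 or 0.8; a second score does not replace the missing tolerance or confirmation rule.

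**Conclusion.** The point holds as an inexpensive improvement to a sound calculation. VHI-10 is measured once before treatment, remotely and about a week early, and that value serves both as the control for the primary test and as the individual threshold for duration. Averaging it with a Day 0 score would trim the detectable difference by about 1-4% and add roughly 1 to 3 percentage points of power. It cuts the individual baseline error SD by a factor of √2, about 29%. The return-to-baseline endpoint benefits more than the primary test, because one value sets the threshold for every survey.

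These sizes rest on the assumed test-retest range, on the plan's SD of 10 (from a 6-week comparison) applying at 8 weeks, on both baseline scores relating equally to the later score, and on normal, independent errors. The schedule facts need no assumption.

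**What to change.** - Add VHI-10, on the same Qualtrics form, to section 9.2 and to the Visit 1 column of Appendix 1, completed before the injection.
- In sections 5.1, 5.2, 14.3 and 14.4, and in the SAP that section 14 says is still to be written, define baseline as the mean of the screening and Day 0 scores for both the 8-week paired test and the time to baseline VHI-10.
- Prespecify a sensitivity analysis using the Day 0 score alone, in case scores shift between the two occasions.
- Report the screening-to-Day 0 change descriptively as a check on short-term stability, and state that it is not an untreated reference for the 8-week change.

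The cost is a 10-item form taking a few minutes at a visit every patient already attends, plus a protocol amendment that needs prior IRB approval under section 16.1. It can help only patients not yet injected.

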9.2 Visit 1 (Clinic Visit, Day 0)

1. Review of birth control history with female participants of childbearing potential.
2. For women of childbearing potential, counsel participants to use adequate birth control methods required during the trial to avoid pregnancy.
3. For women of childbearing potential, urine pregnancy test will be checked prior to injection.
4. Perform a complete physical examination.
5. Perform DAXI injection. Laterality of injection with DAXI will be dependent on the subject's usual injection pattern. If the patient has traditionally been injected on one side, DAXI will be injected on that same

side. If the patient has traditionally been injected unilaterally but with alternating sides, DAXI injection will follow the alternating pattern. If the patient has traditionally received bilateral injections, DAXI will first be injected on the LEFT side, and if a second dose is required, it will be injected on the right.

6. Record any Adverse Experiences during injection
7. Schedule participant for remote follow-up visit in 5 days.

9.3 Visit 2 (Phone Call, Day 5)

1. Phone call to assess clinical improvement
2. Ensure there is absence of dysphagia (using EAT-10 questionnaire), no injection site issue, or other adverse events using safety survey

9.4 Visit 3 (Optional Clinic Visit, Day 7-14)

1. Additional DAXI can be administered in office if the 1st injection does not have desired clinical effect
2. Injection occurs on same side if normally unilateral, or on opposite side if bilateral

9.5 Visit 4 (Phone call, Day 14*)

1. Phone call to assess clinical improvement
2. Ensure there is absence of dysphagia (using EAT-10 questionnaire), no injection site issue, or other adverse event

*Day 14 after most recent DAXI injection

9.6 Visits 5-10 (Remote Survey, every month starting 1 month after most recent injection)

1. Phone call to assess duration of benefit
2. Patient fills out PROMs electronically through Qualtrics to assess our primary (VHI-10) and secondary outcome measures

- VHI-10
 - CPIB-10
 - OMNI-VES
 - EAT-10
3. Patient records their voice in Phonalyze for CPP and CAPE-V analysis
 4. Patient will record whether DAXI still has desired effect

Data is collected monthly until loss of benefit.

For every instance when all PROMs and Phonalyze recordings are completed, patients will be paid \$10, up to \$150. After the completion of the study the number of entries will be tabulated and patient will be given a Visa gift card in the allotted amount. Patients who withdraw from the study will still be compensated for all instances when PROMs and Phonalyze recordings were completed.

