2.1 Risk / Benefit Assessment

Risks are mitigated through the use of fellowship-trained laryngologists who are experts at this type of injection.

Possible Risks: There are risks to taking part in any research study. Some of the most likely risks of participation in this study include:

- Having no effect on voice
- Requiring multiple injections
- Injection site pain or discomfort

There are also rare but serious risks of participation, like:

- *Difficulty swallowing, possibly requiring a temporary feeding tube*
- *Difficulty breathing, possibly requiring hospitalization*

Possible Benefits:

- Participants may benefit from participating in the study, but this cannot be guaranteed. When looking at previous trials with a different indication, DAXI provided a longer-lasting effect than traditional Botox.

The potential benefits may outweigh the risks as DAXI may ultimately decrease frequency of injection, while maintaining similar risk to Botox injection.

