5.2 Secondary Efficacy Endpoints

The secondary endpoint is duration of benefit, assessed by median time to baseline VHI-10 after treatment with DAXI and via phone call surveys. VHI-10 questionnaires will be given at baseline, day 14, then monthly until loss of benefit. Phone calls will be conducted at day 5, day 14, then monthly until loss of benefit.

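### No early safety call is scheduled after an optional second DAXI injection: the first planned check comes at 14 days, against 5 days after the first injection

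*Combined protocol and SAP*

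**What the plan says.** **After dose 1.** The last step of Visit 1 (section 9.2, item 7) is "Schedule participant for remote follow-up visit in 5 days". Visit 2 (section 9.3) carries this out on Day 5. It asks about clinical improvement and, as a separate item, requires staff to "Ensure there is absence of dysphagia (using EAT-10 questionnaire), no injection site issue, or other adverse events using safety survey".

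**Dose 2.** Visit 3 (section 9.4, Day 7-14) is optional and is for patients in whom the first injection fell short. Section 4.1 puts the additional dose at one week. The dosing table in section 7.4.1 makes dose 2 equal to dose 1 in units. On the side, section 9.4 says "Injection occurs on same side if normally unilateral, or on opposite side if bilateral". For usually bilateral patients section 7.4.3 adds that "DAXI will first be injected on the left side, and if a second dose is required, it will be injected on the right". Section 9.4 has no step that books a follow-up.

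**After dose 2.** Section 9.5 sets Visit 4 at "Day 14 after most recent DAXI injection". The overall call schedule in section 5.2 is "Phone calls will be conducted at day 5, day 14, then monthly until loss of benefit", with no repeat of the Day 5 call. Appendix 1 shows none either, and gives Visits 1 to 4 a ±2-day window. The monthly contacts of section 9.6 start one month after the most recent injection, so they come later than Visit 4.

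**Risks named.** Section 2.1 lists two rare but serious risks: swallowing difficulty that may need a temporary feeding tube, and "Difficulty breathing, possibly requiring hospitalization".

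**The concern.** The protocol includes an active check for dysphagia and other adverse events within a week of dose 1. It does not repeat that check after dose 2, although cumulative exposure is then higher.

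- **Usually unilateral patients:** dose 2 goes to the same side, so that side receives twice the usual nominal units within about two weeks.
- **Usually bilateral patients:** dose 2 goes to the other side. The per-side dose does not rise, but total units double and both sides carry DAXI for the first time.

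Active questioning about adverse events is tied to visits (section 10.1). The investigator team's review, at least every two weeks, looks for voice, swallowing and breathing problems in survey data (section 13), and none are scheduled between dose 2 and Visit 4. Events that a patient does not volunteer would be found later, and their onset and duration would rest on recall at about two weeks. The synopsis plans to report time of onset, duration and reversibility of toxicities, so the quality of those dates matters.

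**Working it through.** No sample-size formula bears on this point; the check is date and dose arithmetic on the visit schedule. It assumes that Visit 2 takes place before Visit 3, as the numbering implies.

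**Inputs.** Visit 2: Day 5 (section 9.3). Visit 3: Day 7-14 (section 9.4). Visit 4: 14 days after the most recent injection (section 9.5). Window: ±2 days (Appendix 1). Doses: 0.625, 1.25 or 2.5 units, with dose 2 equal to dose 1 (section 7.4.1).

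**Time to first planned safety contact**

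| | Nominal | With window |
|---|---|---|
| After dose 1 (Visit 2) | 5 days | 5 ± 2 = 3-7 days |
| After dose 2 (Visit 4) | 14 days | 14 ± 2 = 12-16 days |
| Difference | 14 − 5 = 9 days | 12 − 7 = 5 to 16 − 3 = 13 days |

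**Study day of Visit 4 in a re-injected patient.** Nominal: 7 + 14 = 21 to 14 + 14 = 28. Applying the window to Visit 3 as well (Day 5-16): 5 + 12 = 17 to 16 + 16 = 32. On the one-week timing in section 4.1, dose 2 is on Day 7 and Visit 4 on Day 21. The 9-day difference is the same in every case.

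**Alternative reading of Visit 4.** The Appendix 1 header for Visit 4 says only Day 14. Counted from Day 0, the call would come 14 − 7 = 7 days (5-9) after a Day 7 second dose, but 14 − 14 = 0 days after a Day 14 second dose. It could not serve reliably as follow-up, and section 9.5 states the anchor explicitly.

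**Nominal units after dose 2**

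| Usual pattern | Units on the injected side | Total DAXI units |
|---|---|---|
| Unilateral, same side | 2 × 0.625 = 1.25; 2 × 1.25 = 2.5; 2 × 2.5 = 5.0 | 1.25; 2.5; 5.0 |
| Bilateral, other side | 0.625; 1.25; 2.5 (unchanged) | 1.25; 2.5; 5.0 |

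Two qualifications apply. The table in 7.4.1 does not say whether a listed bilateral BotoxA dose is per side; if it is, dose 2 only returns bilateral patients to their usual nominal units. For unilateral patients who alternate sides, section 9.4 implies the same side for dose 2, whereas the sequence rule in 7.4.3 could mean the other side, in which case their per-side dose does not double. Neither affects the timing.

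**With a call 5 ± 2 days after dose 2.** It would fall on study Day 7 + 5 = 12 to 14 + 5 = 19 (with windows, 5 + 3 = 8 to 16 + 7 = 23). First planned contact would then be 3-7 days after either dose.

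**The case against.** The schedule arithmetic is not in dispute. The case against acting on it has four parts.

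1. **No evidence that 14 days is too late.** The documents give no onset times for the serious risks. The first listed purpose of Visit 2 is to judge improvement ahead of the re-dosing decision, and that purpose ends once dose 2 is given. This stands as far as it goes: the only yardstick is the plan's own Day 5 check. But the safety item in Visit 2 is separate, and its purpose does not end with dose 2.
2. **Other routes exist.** Adverse events are captured throughout (8.1.9), serious events are reported immediately (10.2.1), and patients' calls to the Center are reviewed (section 13). Severe swallowing or breathing trouble would probably prompt a call. This stands, and it limits the gap mainly to milder or unvolunteered events. All these routes depend on the patient making contact.
3. **Re-injected patients are selected.** They had too little effect from dose 1 and have already passed a Day 5 check. Doubling is also nominal, because the protocol matches BotoxA and DAXI units one to one without stating equal potency. This is fair and tempers the concern about dose, but it does not explain a longer wait after dose 2.
4. **The size is unknown and no endpoint is touched.** The number re-injected is not stated. This is true, and it is why the point is a modest improvement and not a flaw in the trial's inference.

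**Conclusion.** The concern holds. As written, the first planned safety contact is 14 days (12-16) after a second injection, compared with 5 days (3-7) after the first: 9 days later, range 5-13. Sections 5.2, 9.4 and 9.5 and Appendix 1 do not close the gap. The conclusion rests on section 9.5 governing the timing of Visit 4 and on the Day 5 call being the plan's own standard for early safety contact. It does not rest on any assumed onset time or on potency equivalence. The number of patients affected lies between 0 and 20. The effect is confined to the timeliness and dating of adverse events after dose 2; the primary endpoint, its analysis and the power calculation are unchanged. It should be corrected because it concerns the highest cumulative exposure in the trial and costs little.

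**What to change.** Keep Visit 2 at Day 5 after dose 1 and Visit 4 at 14 days after the most recent injection. Add one phone call 5 ± 2 days after any Visit 3 injection, using the EAT-10 and the 7-item safety survey in Appendix 4. Book it at Visit 3, as section 9.2 item 7 does after dose 1.

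Amend sections 5.2, 9.4 and 9.5 and Appendix 1 to show the call. In the same edit, name the safety survey at Visit 4, since section 9.5 omits it although section 9.3 includes it, and repeat the most-recent-injection anchor in the Appendix 1 header.

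The cost is one short call per re-injected patient, at most 20 × 1 = 20 calls, with existing questionnaires and no additional clinic visit. The amendment needs written IRB approval before it takes effect (section 16.1).

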9.7 Early Withdrawal Visit

N/A

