11 DISCONTINUATION AND REPLACEMENT OF PARTICIPANTS

11.1 Early Discontinuation of Study Drug

A subject may be discontinued from study treatment at any time if the subject, the investigator, or the Sponsor feels that it is not in the subject's best interest to continue. The following is a list of possible reasons for study treatment discontinuation:

- Subject withdrawal of consent
- Subject is not compliant with study procedures
- Adverse event that in the opinion of the investigator would be in the best interest of the subject to discontinue study treatment
- Protocol violation (falsifying eligibility criteria) requiring discontinuation of study treatment
- Lost to follow-up
- Positive pregnancy test (females)

If a subject is withdrawn from treatment due to an adverse event, the subject will be followed and treated by the Investigator until the abnormal parameter or symptom has resolved or stabilized.

All participants who discontinue study treatment should come in for an early discontinuation visit as soon as possible and then should be encouraged to complete all remaining scheduled visits and procedures.

All participants are free to withdraw from participation at any time, for any reason, specified or unspecified, and without prejudice.

Reasonable attempts will be made by the investigator to provide a reason for subject withdrawals. The reason for the subject's withdrawal from the study will be specified in the subject's source documents.

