13 DATA SAFETY MONITORING

A Data Monitoring Committee (DMC) to review data relating to safety and efficacy, to conduct and review interim analyses, and to ensure the continued scientific validity and merit of the study, according to the UCSF IRB. The DMC will be made up of the investigator team (PI, other study clinicians, and research assistants) will be meeting at least every 2 weeks to review preliminary data. At this time, the following will be reviewed:

- Enrollment (number of participants)

- Adverse events
- Any unexpected voice/swallow/breathing problems based on the survey data collected
- Any phone calls by participants to the Voice and Swallowing Center
- Breaches of confidentiality
- Unanticipated problems

This information will be shared with the UCSF IRB every 6 weeks. If there are any adverse events or unanticipated problems, this will be communicated immediately. An interim analysis will be conducted and reported three months after the study start date, or after the 10th subject is recruited, whichever comes first. Any participants whose confidentiality has been breached will be notified as soon as possible.

A study subject's participation in the trial will be withdrawn immediately for any the following criteria:

- The patient wishes to end participation
- The patient undergoes an additional laryngeal Botox injection (at UCSF or elsewhere)
 - Unrelated medical event/condition which impacts voice/swallowing
- The trial will be halted immediately for any of the following events:
 - If a pattern of poor clinical outcomes is seen
 - For multiple adverse events
 - At UCSF IRB discretion

Based on UCSF IRB guidelines, this trial does not meet criteria for a Data Safety Monitoring Board, although one would be assembled if requested by the UCSF IRB. The study has none of the following features:

- There is a significant likelihood of a serious adverse event to participants
- The study is conducted at multiple sites and the level of risk is greater than minimal
- The study generates data that are blinded or randomized
- The study involves a large number of patients randomized to one of two or more interventions

- A study for which the performance of an interim analysis is crucial for the protection of the participants
- First use in humans
- First use in children
- The study involves gene therapy, stem cell therapy, or other novel interventions for which long-term outcome data are not known or available

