APPENDIX 1. STUDY VISITS

	SCREENING	VISIT 1 (CLINIC VISIT, DAY 0) ^a	VISIT 2 (PHONE CALL, DAY 5) ^a	VISIT 3 (OPTIO NAL CLINIC VISIT, DAY 7- 14) ^a	VISIT 4 (PHONE CALL, DAY 14) ^a	VISIT 5-10 (STARTING 1 MONTH AFTER LAST DAXI INJECTION, MONTHLY UNTIL LOSS OF BENEFIT)
Informed Consent	X					
Medical History	X					
Urine pregnancy test (if applicable)		X				
Physical Exam		X				
DAXI Injection		X		X		
USDRS		X		X		
Phone call to assess duration of benefit			X		X	X
EAT-10	X		X		X	
VHI-10	X				X	X
OMNI-VES	X				X	X
CPIB-10	X				X	X
Phonalyze recording	X				X	X

^a ±2 days

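### VHI-10 collection ends at loss of benefit, so a subject who fails by month 1 has no scheduled week-8 score and the primary estimate leans toward benefit

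*Combined protocol and SAP*

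**What the plan says.** Section 5.1 defines the endpoint: "The primary efficacy endpoint is the difference in VHI-10 scores at 8 weeks after injection with DAXI". Section 14.3 gives the test: "This will be determined using a paired t-test with subjects pre-treatment VHI-10 scores as a control". Each subject therefore needs both a baseline and a week-8 score.

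Three places end collection on the outcome:
- Section 9.6: "Data is collected monthly until loss of benefit".
- Section 5.2: "VHI-10 questionnaires will be given at baseline, day 14, then monthly until loss of benefit".
- Appendix 1, column for Visits 5-10: "MONTHLY UNTIL LOSS OF BENEFIT".

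Two places point the other way. Section 5.1 has VHI-10 continuing monthly with no stopping condition, and section 4.1 gives total participation as 36 weeks (the synopsis says up to 36).

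On subjects who leave early, section 11.1 says: "All participants who discontinue study treatment should come in for an early discontinuation visit as soon as possible". Section 9.7 marks the early withdrawal visit as not applicable. Section 13 withdraws a subject at once after a further laryngeal Botox injection. Section 14.1 defines only a safety set. Section 14 defers details to a later SAP. The plan gives no efficacy set, no rule for missing scores and no allowance for dropout.

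**The concern.** Subjects are asked about benefit at day 5, day 14 and month 1, all before week 8. If one of them says at or before month 1 that benefit is absent or gone, sections 5.2 and 9.6 and Appendix 1 schedule no further VHI-10. A paired t-test with no missing-data rule then leaves that subject out.

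The reason for the missing score is the outcome itself. Those who remain are, on average, the ones still doing well, so the mean change leans toward benefit. The trial has one arm, so no control group carries the same distortion. A later SAP can choose an analysis but cannot recover scores that were never collected. Section 2.1 lists absence of any voice effect among the most likely risks, so such subjects cannot be assumed away.

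**Working it through.** **1. The plan's power figure.** Inputs from section 14.6: n = 20, difference 6.6, SD of the difference 10, alpha 0.05 (sidedness not stated). Noncentrality = (6.6/10) × √20 = 2.95 on 19 df. Two-sided power is 79.9%, which reproduces the stated 80%.

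**2. Who is lost.** In section 9.6 the questionnaires and the report on whether DAXI still works belong to the same monthly contact. A subject who first reports loss at month 2 can still supply that score. The subjects at risk are those reporting loss at or before month 1. I take month 1 as 365.25/7/12 = 4.35 weeks and the month-2 contact as the week-8 assessment.

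**3. How many.** The documents give no DAXI duration in this disease. As an assumption I use the two Botox durations in section 14.6 and three distribution shapes. Each entry is the share p with duration under 4.35 weeks.

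| Source (mean/SD, weeks) | Lognormal | Gamma | Normal |
|---|---|---|---|
| Institution, 18.9/7.2 | 0.01% | 0.15% | 2.2% |
| Retrospective study, 15.1/12.3 | 8.2% | 16.5% | 19.1% |

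The 19.1% is an upper end: that normal curve puts Φ(−15.1/12.3) = 11.0% of durations below zero. Truncated at zero it gives (19.1 − 11.0)/(100 − 11.0) = 9.1%. In subjects out of 20, the institution's figures give 0 to 0.4 and the retrospective study's give 1.6 to 3.3 (3.8 on the untruncated normal).

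**4. Bias.** Let μ be the true mean improvement in all treated subjects and d the mean improvement among those lost. Then μ = (1 − p)m + pd, so the complete-pair mean is m = (μ − pd)/(1 − p). Sections 5.2 and 14.4 treat the end of benefit as return to baseline VHI-10, which corresponds to d = 0 and m = μ/(1 − p). With μ = 6.6:
- p = 0 to 2.2%: m = 6.6 to 6.6/0.978 = 6.7.
- p = 8.2%: 6.6/0.918 = 7.2.
- p = 16.5%: 6.6/0.835 = 7.9.
- p = 19.1%: 6.6/0.809 = 8.2.

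**5. False positives.** With μ = 0 the bias is −pd/(1 − p). At d = 0 this is zero and the one-sided rate stays at 2.5%. It rises only if d is negative.

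**6. Loss of pairs.** Power for a fixed 6.6-point mean, SD 10, two-sided 0.05:

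| Pairs | 20 | 19 | 18 | 17 | 16 |
|---|---|---|---|---|---|
| Power | 79.9% | 77.7% | 75.2% | 72.4% | 69.4% |

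**The case against.** The strongest reply has four parts.

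- Section 5.1, which defines the primary endpoint, states no stop, so the sponsor could say week-8 scores were always meant to be collected. That is possible, but the visit section and the schedule that staff would follow both stop. At the least the sections conflict over the primary data.
- Subjects without the desired effect may receive a second DAXI injection (sections 4.1 and 9.4), and the monthly contacts restart from the latest injection. This may reduce early failures. It leaves the stopping rule in place for those who still fail.
- Section 14.6 sizes the duration comparison on the institution's figures, under which almost nobody is lost by month 1, and DAXI is hoped to last longer. This stands as a limit on size. However, DAXI's effect in this population is what the trial is testing, so a low failure rate should not be built into data collection.
- Botox re-injection before week 8 looks uncommon, since section 1 gives a typical interval of three months. This also stands; re-injection is the lesser route to a missing score.

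A reader might infer that everyone who fails before week 8 is omitted, which on the retrospective figures would be 28–34%. The documents do not support that, because the month-2 questionnaire and the month-2 report of loss share one contact.

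**Conclusion.** The gap is real. Followed as written, sections 5.2 and 9.6 and Appendix 1 make the week-8 score depend on outcome, and the direction of the bias is toward benefit. Its size cannot be fixed from the documents. It is close to nil on the institution's durations (6.6 reads as 6.6–6.7) and modest on the retrospective study's (7.2–7.9, or 8.2 at the extreme). These figures assume that DAXI lasts as long as Botox, that those lost are at baseline on average, and that the t-test uses complete pairs only.

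A reader might go further and infer a raised false-positive rate. If 19% are missing and all are drawn from subjects with no improvement, simulation gives a rate near 12% and an apparent gain of about 1.9 points when there is no true effect; a true 3 points reads as 5.3. Those results need the missing subjects to average 8.0 and 7.0 points worse than baseline respectively: 0.19 × 8.0/0.81 = 1.9, and (3 + 0.19 × 7.0)/0.81 = 5.3. Nothing in the documents equates loss of benefit with worsening of that order. With those subjects at baseline, 3 points becomes 3/0.81 = 3.7 and the null rate stays nominal.

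**What to change.** 1. Reconcile section 5.1 with sections 5.2 and 9.6 and Appendix 1, so that VHI-10 is collected at the week-8 contact from every subject who received DAXI, whether or not benefit is lost. Name the contact that serves as week 8.
2. Reconcile sections 9.7, 11.1 and 13 for data collection only. After withdrawal or re-injection, keep collecting the remote VHI-10 to week 8 if the subject agrees. This does not touch the rules on treatment.
3. Define the primary analysis set as all treated subjects and use scores as collected. Report how many week-8 scores are missing and how many follow re-injection.
4. Add a sensitivity analysis that sets any missing week-8 score to the subject's baseline value. Collected scores should not be overwritten with zero change. A repeated-measures mixed model is optional.

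Cost: protocol wording and a few extra 10-item online surveys. If the full set is completed, each entry earns $10. Baseline, day 14 and six monthly entries come to 8 × $10 = $80, within the $150 cap. The burden falls on a few subjects whose benefit has ended.
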